7.1 Primary Efficacy Endpoint

Proportion of patients with anterior chamber cell grade of "0" (absence of cells) compared to placebo at Day 8.

Anterior chamber cell grade will be assessed by the investigator during silt-lamp examination and will be graded on an adapted 6-point scale proposed by the Standardization of Uveitis Nomenclature (SUN) working group (23) (Table 2)

Table 2 Grading scheme for anterior chamber cells

Grade	Cells in field†
0	0
0.5+	1-5
1+	6-15
2+	16-25
3+	26-50
4+	>50

[†]Feld size is a 1 mm by 1 mm slit beam

7.2 Key Secondary Efficacy Endpoint

Proportion of patients with VAS pain of "0" (no eye pain) compared to placebo at Day 8.

Eye pain score will be assessed by the patient before any ocular examination and will be scored by ticking on a continuous scale comprised of a 10 cm (100 mm) horizontal line anchored by two verbal descriptions: "no eye pain" (score of 0) and "worst imaginable eye pain" (score of 10).

7.3 Other Secondary Efficacy Endpoints

Other secondary efficacy endpoints will be:

- Proportion of patients with anterior chamber cell grade of "0" compared to placebo at Day 3, Day 15 and Day 29
- Change from Baseline to Day 3, Day 8, Day 15 and Day 29 compared to placebo in the proportion of patients with different anterior chamber cell grades
- Change from Baseline to Day 3, Day 8, Day 15 and Day 29 compared to placebo in the proportion of patients with different anterior chamber flare grades
- Proportion of patients with anterior chamber cell grade of "≤0.5+" and flare grade of "0" compared to placebo at Day 3, Day 8, Day 15 and Day 29
- Proportion of patients with anterior chamber cell grade of "≤1+" compared to placebo at Day 3, Day 8, Day 15 and Day 29
- Proportion of patients with anterior chamber cell grade of "0" and flare grade of "0" compared to placebo at Day 3, Day 8, Day 15 and Day 29
- Frequency of different signs of ocular inflammation compared to placebo at Baseline, Day 3, Day 8, Day 15 and Day 29
- Change from Baseline to Day 3, Day 8, Day 15 and Day 29 compared to placebo in the proportion of patients with different signs of ocular inflammation
- Change from Baseline to Day 3, Day 8, Day 15 and Day 29 compared to placebo in the severity of signs of ocular inflammation
- Change from Baseline to Day 3, Day 8, Day 15 and Day 29 compared to placebo in the visual analog scale (VAS) photophobia score
- Change from Baseline to Day 8, Day 15 and Day 29 compared to placebo in Snellen best-corrected visual acuity (BCVA) score

- Change from Baseline to Day 3, Day 8, Day 15 and Day 29 compared to placebo in the VAS pain score
- Proportion of patients with VAS pain of "0" compared to placebo at Day 3, Day 15 and Day 29
- Change from Baseline to Day 3, Day 8, Day 15 and Day 29 compared to placebo in the proportion of patients with different discomfort grades
- Proportion of patients with no discomfort ("None") compared to placebo at Day 3, Day 8, Day 15 and Day 29
- Change over time in the VAS pain score reported in the patients' diaries compared to placebo

7.3.1 Secondary efficacy assessments

See previous Section 7.1 for anterior chamber cell grade.

 Anterior chamber cell flare will be assessed by the investigator during slit-lamp examination and will be graded on a 5-point scale proposed by the SUN working group (23) (Table 3)

Table 3 The SUN working group grading scheme for anterior chamber flare

Grade	Description
0	None
1+	Faint
2+	Moderate (iris and lens details clear)
3+	Marked (iris and lens details hazy)
4+	Intense (fibrin or plastic aqueous)

- Signs of ocular inflammation (chemosis, bulbar conjunctival injection, ciliary injection, corneal edema, keratic precipitates) will be assessed by the investigator during slitlamp examination. Additionally, the severity of these signs of ocular inflammation will be assessed (see Appendix 2)
- The IOP will be assessed in both eyes using the Goldmann applanation tonometry method (see Appendix 3)
- Monocular visual acuity will be completed with the patient's best correction vision in place using standard of care Snellen chart
- The eye pain VAS is a single-item continuous scale comprised of a 10 cm (100 mm) horizontal line anchored by two verbal descriptors, one for each symptom extreme. For eye pain intensity, the scale is anchored by "no eye pain" (VAS score of 0) and "worst imaginable eye pain" (score of 100 mm)

The eye pain VAS is completed by the patient. Details and instructions for use of eye pain VAS can be found in Appendix ${\bf 4}$

- The eye discomfort will be assessed by using the categorical scale which can be found in Appendix 5
- The photophobia VAS is a single-item continuous scale comprised of a 10 cm (100 mm) horizontal line anchored by two verbal descriptors, one for each symptom extreme. For photophobia intensity, the scale is anchored by "no photophobia" (score of 0) and "worst imaginable photophobia" (score of 100 mm)

The photophobia VAS is completed by the patient. Details and instructions for use of photophobia VAS can be found in Appendix 6

7.4 Secondary Safety Endpoints

The secondary safety endpoints will be:

- Number, frequency and severity of AEs up to Day 29
- Number, frequency and severity of Serious AE (SAE) up to Day 29
- Proportion of patients discontinuing the study due to AEs
- Proportion of patients discontinuing the study due to lack of efficacy
- Change from Baseline to Day 3, Day 8, Day 15 and Day 29 compared to placebo in IOP
- Change from Baseline to Day 3, Day 8, Day 15 and Day 29 compared to placebo in physical and eye examination parameters and vital signs
- Use of concomitant medications up to Day 29

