- 16) Presence of Fuchs´ endothelial dystrophy (loss of endothelial cells that may result in chronic corneal edema after cataract surgery especially if high energy was used during phacoemulsfication)
- 17) Presence of cornea guttata
- 18) Pupil dilation lower than 4.5 mm
- 19) Presence of lower lacrimal duct obstruction and/or history of infectious dacryocystitis
- 20) Presence of IOP ≥24 mmHg in the study eye at Visit 1
- 21) Participation in any study of an investigational topical or systemic new drug or device within 30 days prior to the Screening visit (Visit -1), or at any time during the study
- 22) Prior participation in the study described in this protocol, unless patient was not randomized
- 23) In the opinion of the investigator or study coordinator, be unwilling or unable to comply with study protocol or unable to successfully instill eye drops
- 24) Disease, condition (including monocular patients), or disorder that in the judgement of Investigator could confound study assessments or limit compliance to study protocol

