9. STATISTICAL METHODS

9.1 General Statistical Methods

In general, data will be summarized by means of summary statistics. Continuous data will be presented with the number of observations, mean value, confidence intervals, standard deviation, minimum, Q1, median, Q3 and maximum value. Change from baseline to each post-baseline visit will be also described using descriptive statistics. Categorical data will be presented as counts and percentages.

The data will be presented for each treatment group by visit.

Individual patient data will be listed for all enrolled patients. Listings will be sorted by center and patient number and labelled by randomized treatment group.

Before unmasking the study data, a separate statistical analysis plan (SAP), which will provide the technical details of the statistical analysis outlined below, will be prepared and approved.

For statistical analyses, the following definitions will be applied:

- Baseline: Baseline is defined as Visit 1 (Day 1, 24 h after the cataract surgery).
- Randomized treatment group: The treatment that was assigned at the time of randomization.

The assessments performed at Visit 1 (Day 1) will be considered the baseline values.

All data collected during study follow-up will be displayed and analyzed according to the actual visit data in the eCRF.

Unless otherwise stated, all statistical tests will be conducted using two-sided alpha = 0.05.

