3.3 Secondary Safety Endpoints

- Number, frequency and severity of adverse events (AEs) up to Day 29.
- Number, frequency and severity of serious AEs (SAEs) up to Day 29.
- Proportion of patients discontinuing the study due to AEs.
- Proportion of patients discontinuing the study due to lack of efficacy.
- Change from Baseline to Day 3, Day 8, Day 15 and Day 29 compared to placebo in intraocular pressure (IOP).
- Change from Baseline to Day 3, Day 8, Day 15 and Day 29 compared to placebo in physical and eye examination parameters and vital signs.
- Use of concomitant medications up to Day 29

The IOP will be assessed in both eyes using the Goldmann applanation tonometry method (for details see Appendix 3 of CSP).

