6.3.2 Summary Statistics

Data will be summarised by means of summary statistics. For continuous data the following summary statistics will be presented: number of observations, mean, standard deviation (SD), minimum, Q1, median, Q3 and maximum. 95% CI of the mean will also be presented for efficacy and safety data. Change from baseline to each post-baseline visit will be also described using descriptive statistics. Categorical data will be presented as counts and percentages.

Summary statistics will be presented by treatment group and visit, as applicable.

Certain presentations (withdrawals, patient exclusion from datasets, baseline and background characteristics and primary efficacy data) may be broken down by study center, if relevant.

All data collected during study follow-up will be displayed and analyzed according to the actual visit data in the eCRF.

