SAF will be used for all AE related summaries.

As stated in the study protocol, treatment arms will be compared with respect to safety endpoints descriptively only. No further inferential comparison will be carried out.

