14.3 SAFETY DATA

Adverse events

Table	Title	Pop	Top.Line
14.3.1.1	Summary of Treatment Emergent Adverse Events (TEAEs)	SAF	X
14.3.1.2.1	Treatment Emergent Adverse Events by System Organ Class and Preferred Term	SAF	
14.3.1.2.2	Treatment Emergent Ocular Adverse Events by System Organ Class and Preferred Term	SAF	
14.3.1.3	TEAEs by SOC and PT by worst severity	SAF	
14.3.1.4	TEAEs by SOC and PT by worst relationship	SAF	
14.3.1.5	TEAEs related to IMP/Placebo	SAF	
14.3.1.6	TEAEs leading to discontinuation	SAF	
14.3.1.7	Serious TEAEs	SAF	
14.3.1.8	Serious TEAEs related to IMP/Placebo	SAF	
14.3.1.9	TEAEs AESI	SAF	
14.3.1.10	TEAEs AESI related to IMP/Placebo	SAF	
14.3.2	Listings of Deaths Other Serious Adverse Events, and OtherSignificant Adverse Events	SAF	

14.3.3 [This title is reserved for narratives.]

Study Code: CLOBOF3-16IA01 Date: 09-JUL-2021

NCT No.: NCT04246801

Sponsor: Laboratorios Salvat, S.A.

Other Safety assessments

Table	Title	Pop	Top.Line
14.3.4.1	Absolute and Percentage change from Baseline in Vital Signs by treatment regimen. Descriptive Statistics	SAF	
14.3.4.2	Summary statistics. Change from Baseline to Day 3, Day 8, Day 15 and Day 29 compared to placebo in intraocular pressure (IOP).	SAF	X

Treatment exposure

Table	Title	Pop	Top.Line
14.3.5.1	Compliance with IMP/Placebo % (doses/amount). Descriptive statistics.	SAF	
14.3.5.2	Exposure to IMP/Placebo: Duration of treatment Number ofdoses completed/not completed, and reasons by treatment regimen. Descriptive statistics	SAF	

Concomitant medications

Table	Title	Pop	Top.Line
14.3.10.1	Summary of Prior Medications and Therapies tabulated by ATC level 3 group and generic medication name	SAF	
14.3.10.2	Summary of All Concomitant Medications (rescue and prohibited medications included) and Therapies tabulated by ATC level 3 group and generic medication name	SAF	
14.3.10.3	Summary of Concomitant Medications (Rescue and prohibited) tabulated by ATC level 3 group and generic medication name	SAF	

Sponsor: Laboratorios Salvat, S.A. Study Code: CLOBOF3-16IA01 NCT No.: NCT04246801

8.2 Listings of individual patient data and other information to be produced for the clinical study report (sections 16.1 and 16.2 according to ICH E3)

Listing	Title	Pop	Top.Line
16.1.7	Randomisation scheme	ALL	

Patient disposition

Listing	Title	Pop	Top.Line
16.2.1.1	Patient Disposition	ALL	
16.2.1.2	Screening Failures, Discontinued Subjects, Reason for Discontinuation	ALL	X
16.2.1.3	Visits dates		

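### The IOP endpoint is worded as a comparison with placebo, but the SAP specifies no between-arm difference or confidence interval for it and credits the protocol with a descriptive-only rule the protocol does not state

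*Protocol*

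**What the plan says.** - **Endpoint.** Protocol 7.4 lists "Change from Baseline to Day 3, Day 8, Day 15 and Day 29 compared to placebo in IOP". SAP 3.3 carries the same endpoint, again "compared to placebo in intraocular pressure (IOP").
- **Planned output.** The IOP summary table is SAP Table 14.3.4.2, on the SAF and flagged for top-line reporting: "Summary statistics. Change from Baseline to Day 3, Day 8, Day 15 and Day 29 compared to placebo in intraocular pressure (IOP"). SAP 6.3.2 defines the summary statistics as n, mean, SD and quantiles, and adds "95% CI of the mean will also be presented for efficacy and safety data". SAP section 8.1 lays safety tables out by treatment group and timepoint. Individual readings go to Listing 16.2.11. SAP 6.3.11 (Other Safety Assessments) does not mention IOP.
- **Rule on safety comparisons.** SAP 6.3.10 says "As stated in the study protocol, treatment arms will be compared with respect to safety endpoints descriptively only", and then "No further inferential comparison will be carried out".
- **Baseline.** Protocol 9.1 states "Baseline is defined as Visit 1 (Day 1, 24 h after the cataract surgery"). The Visit 1 schedule in Protocol 4.3.2.2 places the IOP reading before the first dose.

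**The concern.** The endpoint asks how IOP change on clobetasol differs from IOP change on vehicle. The plan describes each arm separately and leaves the difference and its uncertainty to the reader.

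This matters more for IOP than for most safety variables. Protocol 8.3.10 singles out IOP rise as an expected adverse reaction that could be severe, and Protocol 8.3.9 makes a rise over 30 mmHg an adverse event of special interest. Each arm's own change starts from a reading taken 24 hours after surgery, so it mixes the post-surgical course of IOP with any drug effect. Randomization makes the first component common to both arms in expectation, and subtracting one arm from the other removes it. The subtraction is the step the plan omits.

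The reason given for stopping at description is a protocol statement. If the protocol contains no such statement, the restriction is the SAP's own choice, and it should be presented and justified as one.

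**Working it through.** **1. Is the rule in the protocol?** Protocol 9.1.13 plans tabulations and listings of adverse events. Protocol 9.1.13.1 plans summaries of examinations and vital signs, with shift tables. The synopsis says safety outcomes are analyzed overall and by arm. None of these limits safety comparisons to description, and none prescribes a test. SAP 6.1, which sets out changes to the planned analyses, does not list the restriction.

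**2. How does the SAP treat identically worded endpoints?** VAS photophobia and VAS pain are also defined as change from baseline to Days 3, 8, 15 and 29 compared to placebo. SAP 6.3.6.2 gives them a repeated-measures model with baseline as covariate and treatment, visit and their interaction as effects (Tables 14.2.12 and 14.2.14). IOP is continuous, is measured at the same visits and has the same endpoint wording, but gets by-arm summaries only. No reason is given.

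**3. What can be derived from the planned table?** The plan gives no precision or power figure for IOP, so there is none to reproduce. Arm sizes are the planned 140 and 70 (Protocol 9.1.1). The documents give no IOP SD or correlation, so the values below are assumptions.

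The unadjusted difference in mean change follows from n, mean and SD:

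- SE = SD of change × √(1/140 + 1/70) = 0.1464 × SD of change.
- 95% half-width = 1.96 × 0.1464 × SD = 0.287 × SD.
- For an SD of change of 2, 3, 4, 5 or 6 mmHg, this is ±0.57, 0.86, 1.15, 1.43 or 1.72 mmHg.
- Check at SD 4: the arm half-widths are 0.66 and 0.94, and √(0.66² + 0.94²) = 1.15.

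**4. What does baseline adjustment add?** Let the IOP SD at each visit be s and the baseline-to-follow-up correlation be r.

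- SD of change = s√(2(1 − r)).
- Residual SD after adjustment = s√(1 − r²).
- Variance ratio = (1 − r²) / (2(1 − r)) = (1 + r)/2, which does not depend on s.

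With s = 3 mmHg:

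| r | SD of change | half-width, unadjusted | residual SD | half-width, adjusted | variance ratio |
|---|---|---|---|---|---|
| 0.2 | 3.79 | 1.09 | 2.94 | 0.84 | 0.60 |
| 0.4 | 3.29 | 0.94 | 2.75 | 0.79 | 0.70 |
| 0.6 | 2.68 | 0.77 | 2.40 | 0.69 | 0.80 |

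Half-widths scale with s. At r = 0.4 they are 0.63 and 0.53 mmHg for s = 2, and 1.26 and 1.05 mmHg for s = 4.

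The adjusted estimate needs the baseline-to-follow-up covariance, which is not among the statistics in SAP 6.3.2.

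**5. A caution on reading the two arm intervals by eye.** Two separate 95% intervals stop overlapping only when the difference exceeds that needed for its own interval to exclude zero by a factor of (1/√140 + 1/√70) / √(1/140 + 1/70) = 0.2040/0.1464 = 1.39. The plan does not say the arms will be judged by overlap, but the two arm intervals are the only intervals it plans.

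**The case against.** **A reader might infer that the SAP prohibits any between-arm estimate.** It does not. SAP 6.3.10 says the arms will be compared, descriptively, and excludes inferential comparison. A descriptive difference is unspecified rather than forbidden. The SAP does not say whether a confidence interval for the difference would count as inferential.

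**A reader might infer that IOP is never set against placebo.** That is also too strong. Both arms appear in one top-line table, and the unadjusted difference with its CI follows by the arithmetic in step 3. Rises over 30 mmHg are tabulated by arm as events of special interest (Tables 14.3.1.9 and 14.3.1.10). Those tables do not replace the endpoint: they capture only large rises, and the treatment-emergent window in SAP 6.3.1 closes at the last dose, while the IOP endpoint runs to Day 29.

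**A reader might infer that surgery raised the Day 1 reading and so hides a drug effect.** The documents do not show that mean IOP at Visit 1 is raised, and they limit how high it can be by excluding "Presence of IOP ≥24 mmHg in the study eye at Visit 1". The baseline is pre-dose and common to both arms, so it does not bias the randomized difference. A general fall after surgery would also show in the placebo column. The point about baseline concerns how one arm's change is read alone.

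**The attribution could be called a loose paraphrase**, since the protocol plans no test or model for safety. That is fair as to intent, but planning no test is not the same as stating a descriptive-only rule.

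**The choice between change score and adjusted difference is only one of precision.** This stands. Both are unbiased under randomization; the adjusted one is narrower.

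**Conclusion.** The gap is real and modest. The endpoint is defined against placebo, the planned output stops at by-arm summaries, and the reason cited for stopping there is not in the protocol. What is missing is a pre-specified difference with its interval. The data to compute one are collected, and nothing here invalidates the safety assessment.

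The gain from specifying the adjusted form is a 20% to 40% smaller variance than the unadjusted change difference, for assumed correlations of 0.6 down to 0.2. In mmHg the gain depends on the assumed SD: at r = 0.4 the half-width falls by about 0.10 for an SD of 2, 0.15 for 3 and 0.21 for 4. The calculation assumes equal SDs at both visits and in both arms, the full planned 140 and 70 patients, and a normal approximation. With 134 and 67 patients the factor 0.287 becomes 0.293, so attrition at the planned rate changes little.

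**What to change.** 1. **SAP 6.3.11 and Table 14.3.4.2.** For each of Days 3, 8, 15 and 29, add the study-eye active-minus-placebo difference in IOP change with a 95% CI. Take it from the repeated-measures model form already in SAP 6.3.6.2, or from ANCOVA, with Visit 1 IOP as covariate, in the SAF. Present it as an estimate without a p-value, and do not carry over that section's fallback to a rank test.
2. **SAP 6.3.10.** Remove the attribution to the protocol. State as the SAP's own decision that safety endpoints are not formally tested, and say that the IOP difference with its CI is allowed as estimation.
3. **Optional.** Tabulate change from Visit -1 (pre-operative) IOP beside change from Visit 1. This helps a reader interpret a single arm, but the endpoint as defined does not require it.

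The cost is SAP wording, one model and four more intervals to report. No patients, visits or measurements are added.

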7.5 Demographic and Other Baseline Characteristics

7.5.1 Demographic and Baseline Data

The following demographic and baseline data will be collected at the Screening Visit (Visit –1):

- Year of birth
- Sex
- Race
- Weight and height. Body mass index (BMI) will be calculated from these

7.5.2 Medical History

A detailed medical history of relevant conditions and procedures will be obtained by the investigator or qualified designee at the Screening visit (Visit -1) and recorded as required in the Medical History section of the eCRF.

Relevant medical history will include any previously diagnosed ophthalmic abnormalities and ocular surgeries (including laser procedures). Additionally, present status of visual function (including patient´s self-assessment of visual status, visual needs, any recent or current visual symptoms, and the use of eyeglasses or contact lens), ocular symptoms (e.g., eyelid swelling, diplopia, redness, photophobia) and past ocular history (e.g. prior eye disease, injuries, surgery and other treatments and medications) will be collected. Relevant medical history at Visit 1 (Day 1) will cover the time from the Visit -1 (Screening). For following visits, any medical events

of significance that occurred after the signing of informed consent will be recorded on the corresponding AEs section of the eCRF, except the routine cataract surgery at Day -1.

The medical history classification will be based in the Medical Dictionary for Regulatory Activities (MedDRA) (latest version available) and system organ class (SOC) and preferred term (PT) will be also provided.

7.5.3 Prior and Concomitant Medication

Prior medications taken within 2 months prior to the Screening visit (Visit -1) (36 months prior for ocular implants and/or intravitreal injections) will be recorded at the Screening Visit (Visit -1), including OTC products.

Concomitant medications (including OTC products) and its duration will be recorded in the concomitant medication log/section of the eCRF throughout the study.

Prior medication is defined as medication received prior to first IMP intake. Any medication received at least once after the first IMP intake will be considered as concomitant medication. This means, a medication might be assigned to both, prior and concomitant medication. If no unambiguous assignment to prior and concomitant medication is possible due to incomplete or missing dates, the medication will be assigned to both, prior and concomitant medication.

8. ASSESSMENTS OF SAFETY

AEs will be recorded during the whole study period. For further information of definitions and reporting of AEs and SAEs, see Section 8.3 below.

